4.6 Secondary endpoints

The secondary endpoints will be compared between groups in the mITT population, PP population, and AT population.

- Operating time, continuous variable, measured in minutes;
- Total blood loss during operation, continuous variable, measured in milliliters;
- Conversion to open surgery, categorical variable;
- Postoperative complications, categorical variable. It will be analyzed according to the overall occurrence. The occurrence of its subtype (anastomotic leakage, bowel obstruction, etc.) will also be analyzed. Additionally, Clavien–Dindo classification will be analyzed (\leq grade II, \geq grade III). (3)
- Completeness of specimens, categorical variable. It is evaluated according to the West classification (mesocolic plane, intramesocolic plane, and muscularis propria plane).(4)
- Number of lymph nodes dissected, continuous variable.
- The pathological TNM stage (as per the American Joint Committee on Cancer

Cancer Staging Manual, 8th edition), categorical variable. The T stage, N stage, and TNM stage will be analyzed separately.

- Postoperative recovery, continuous variable. It includes the time to first flatus, the time to first defecation, the time to start food intake, and the postoperative hospital stay. Additionally, the time to first ambulation and the time to remove the abdominal drainage tube, which are not included in the study protocol's design, will also be analyzed. These are measured in days.
- Length of incision, continuous variable. It is measured in millimeters.
- Visual analog score (VAS) of pain, it will be analyzed as categorical variable: no to mild pain (0–3 points); moderate pain (4–6 points), and severe pain (7–10 points).
- 3-year DFS: DFS is defined as the time from randomization until the occurrence of local recurrence, distant metastasis, or death from the tumor, whichever comes first. It is measured in months. For patients who are lost to follow-up, DFS will be censored at the time of the last available tumor assessment before the missing assessments.
- 5-year OS: OS was defined as the time from randomization to death due to any cause. It is measured in months. For patients lost to follow-up, OS will be censored at the time of the last available follow-up prior to the missing assessments.

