(8) Length of incision: The incision length is measured with an aseptic ruler at the end of the surgery, after the incision is sutured. It is measured in millimeters.

(9) Visual analog score (VAS) of pain: Pain severity was assessed 48 hours after the operation using a ruler about 10 cm long. The ruler is numbered from 0 to 10. 0–3 points indicate no to mild pain. 4–6 points represent moderate pain. 7–10 points stand for severe pain.

(10) 3-year disease-free survival (DFS) and 5-year overall survival (OS): DFS was defined as the time from randomization until the discovery of local recurrence, distant metastasis, or

death from the tumor. OS was defined as the time from randomization to death due to any cause.

4. Study design

[figure not shown]

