The patient's surgery-related complications and Clavien–Dindo grade within 30 postoperative days will be recorded. The overall follow-up period for patients after surgery is 5 years, which includes 5-year overall survival (OS) and 3-year disease-free survival (DFS). For patients with recurrent tumors, follow-up should continue for at least 3 years after recurrence or metastasis is discovered or until death.

Appropriate strategies will be used to improve patient adherence and ensure data integrity. When signing the informed consent form, all participants will be informed of the study procedures, potential benefits, and risks to make them fully understand the inconvenience and significance of data collection.

In addition, patients who have had abdominal surgery need to return to our hospital for other treatment of combined injuries, including suture removal. Our medical team will provide standard post-operative care for enrolled participants to promote their adherence.

Investigators will contact patients 1 week before the follow-up session to increase the attendance rate. Patients who miss a scheduled appointment will be contacted to reschedule another appointment within 1 week. Telephone follow-up calls, WeChat group discussions, and personal interviews will be used to maximize retention and complete follow-up.

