12.3.2 Secondary endpoint analysis

The analysis of the secondary endpoints will be carried out in the mITT population. In the analysis of secondary endpoints, categorical variables will be reported as frequencies and percentages. Groups will be compared using the χ^2 test or Fisher's exact test. Absolute risk differences and the corresponding 95% CI will be calculated. Continuous variables will be described as mean \pm standard deviation or median (quartile). Groups will be compared using the t-test or Mann-Whitney U test, as appropriate. Hodges-Lehmann method will be used to calculate the difference in median and the corresponding 95% CI.

The comparison of 3-year DFS and 3-year OS between the two groups will utilize the Kaplan-Meier curve and the Cox proportional risk model. Relevant risk factors will be adjusted in Cox proportional risk model.

The missing data in this trial is expected to be minimal. If it occurs, it will be treated as censored data and not imputed. All statistical tests were 2-sided, and statistical significance was set at $P < 0.05$. All statistical analyses were performed using R or SPSS.

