4.1 General calculation rules

All statistical tests were 2-sided, and statistical significance was set at $P < 0.05$. All statistical analyses were performed using R or SPSS. P-values will be quoted to three decimal places. Confidence intervals (CI) will be two-sided and 95%. CI will also be quoted to one decimal place.

Categorical variables will be reported as frequencies and percentages. Percentages will be quoted to one decimal place. Chi-square tests in contingency tables will be replaced by Fisher's exact tests if any expected cell frequency is less than five.

Absolute risk differences and the corresponding 95% CI will be calculated.

Continuous data with normal distribution were presented as mean (standard deviation) and analyzed by Student's t-test. Continuous variables with non-normal distribution were reported as medians (quartile) and compared using the Mann-Whitney U test. Hodges-Lehmann method will be used to calculate the difference in median and the corresponding 95% CI. Data will be quoted to one decimal place.

Survival data between two groups will be compared using a two-sided log-rank test stratified by pathological TNM (0–I, II, III) and age (≤ 65 years and > 65 years). The hazard ratio (HR) for disease recurrence or death will be estimated using the stratified Cox proportional hazards model, including strata of pathological TNM (0–I, II, III) and age (≤ 65 years and > 65 years). The 95% confidence interval for the HR will be constructed. Results from an unstratified analysis will also be provided. The Kaplan-

Meier methodology will be applied to estimate the median disease-free survival (DFS) and overall survival (OS) for each treatment arm. Kaplan-Meier curves will be developed.

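### DFS leaves out deaths not due to the tumor, the hazard-ratio wording does not match that definition, and the only Kaplan-Meier number named for 3-year DFS and 5-year OS is a median unlikely to be reached

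*Combined protocol and SAP*

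**What the plan says.** **DFS event.** SAP 4.6: "DFS is defined as the time from randomization until the occurrence of local recurrence, distant metastasis, or death from the tumor, whichever comes first". Protocol v2.1, 3.2.2(10), lists the same events and sets the two death rules next to each other: "death from the tumor. OS was defined as the time from randomization to death due to any cause".

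**DFS censoring.** SAP 4.6 gives one rule: "For patients who are lost to follow-up, DFS will be censored at the time of the last available tumor assessment before the missing assessments".

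**Hazard ratio.** SAP 4.1: "The hazard ratio (HR) for disease recurrence or death will be estimated using the stratified Cox proportional hazards model". It names no cause of death and does not say whether the sentence refers to DFS, OS or both.

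**Kaplan-Meier output.** SAP 4.1 uses the method to "estimate the median disease-free survival (DFS) and overall survival (OS) for each treatment arm", and plans curves, a stratified log-rank test and 95% CIs.

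**Time points.** Protocol 3.2.2(10), protocol 7.3 and SAP 4.6 name 3-year DFS and 5-year OS. Protocol 12.3.2 has a different OS time point: "The comparison of 3-year DFS and 3-year OS between the two groups".

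**Exits.** Exit criterion 5 (protocol 5.3) covers patients who for any reason cannot complete the study plan and follow-up. Protocol 12.2.1 and SAP 4.2.1 remove patients who meet an exit criterion from the mITT population.

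**The concern.** The trial compares two ways of making an anastomosis, and anastomotic leak counts as organ/space SSI. A death from leak or sepsis is the kind of death most plausibly linked to the technique, yet DFS as defined does not count it. If such deaths are censored, the reported 3-year DFS exceeds the share of patients alive and free of recurrence, and a difference between arms in these deaths hardly shows in DFS. Because the hazard-ratio wording in SAP 4.1 is not limited to tumor death, two analysts could fit different DFS models and each claim to follow the SAP.

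Separately, an endpoint named for a time point should yield an estimate at that time point. A report that follows SAP 4.1 literally would give a median that is probably not reached, a curve and a hazard ratio, but no 3-year DFS or 5-year OS figure with its CI.

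**Working it through.** The documents give no recurrence rate, mortality rate or power for DFS or OS, so there is no survival figure to reproduce. The only stated size is for SSI: (1.96 + 0.84)² × (0.133×0.867 + 0.080×0.920) / (0.053 + 0.05)² gives 140 per arm, and 140/0.8 = 175, or 350 in total. It reproduces and does not depend on this point.

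**1. Status of a recurrence-free non-tumor death**

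- The DFS definition does not list it, so it is not an event.
- The censoring rule covers loss to follow-up. A patient known to have died is not lost.
- The missing-data rules (protocol 12.3.2, SAP 5) do not apply, because a known death is not missing.
- What remains unstated is whether it is censored or competing, and how cause of death is decided.

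**2. Effect on 3-year DFS (rates assumed)**

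Let r be the 3-year cumulative incidence of recurrence or tumor death, and q that of recurrence-free non-tumor death, with constant hazards. DFS counting any death is S = 1 − r − q. Kaplan-Meier with these deaths censored is exp[ln(S) × r/(r+q)]. Treating them as competing gives 1 − r.

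| r | q | Any death | Censored | Gap (points) | Censored vs competing (points) | Events left out, q/(r+q) |
|---|---|---|---|---|---|---|
| 15% | 1% | 84.0% | 84.9% | 0.9 | 0.1 | 6.3% |
| 15% | 3% | 82.0% | 84.8% | 2.8 | 0.2 | 16.7% |
| 25% | 1% | 74.0% | 74.9% | 0.9 | 0.1 | 3.8% |
| 25% | 3% | 72.0% | 74.6% | 2.6 | 0.4 | 10.7% |

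With 175 per arm, 1-3% is about 2 to 5 patients (1.75 to 5.25). A wider assumption, with 1-8% non-tumor mortality taken as a net 3-year probability, gives a gap of 0.75×0.01 = 0.75 points to 0.85×0.08 = 6.8 points. The choice of event drives the gap; the choice between censoring and competing risk matters far less.

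**3. An imbalance between arms (assumed)**

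Take r = 20% in both arms and q = 1% versus 3%.

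- Any death counted: 79.0% − 77.0% = 2.0 points; HR = ln(0.77)/ln(0.79) = 1.11.
- Non-tumor deaths censored: 79.89% − 79.67% = 0.2 points; HR = 1.01.
- The 95% CI half-width of a difference, 1.96 × √[2p(1−p)/n], is 10.1 points at p = 0.75 and n = 140, and 7.5 points at p = 0.85 and n = 175.

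Both differences lie well inside that half-width. The issue is what is reported, not a detectable effect.

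**4. Can the median be reached in 60 months?**

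The median falls by month 60 only if 3-year DFS is at or below 0.5^[(36/60)^k], where k is the Weibull shape.

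- k = 1 (exponential): 66.0%.
- k = 0.7: 61.6%.
- k = 0.5: 58.5%.

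At a 3-year DFS of 80% (assumed, exponential) the median is 36 × ln(0.5)/ln(0.8) = 112 months. Median OS within 5 years needs 5-year OS of 50% or lower. Entry is limited to M0 disease, and distant metastasis found at surgery or on pathology is an exit criterion, so neither threshold is likely to be crossed.

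**The case against.** The DFS definition is the same in protocol v1.0, protocol v2.1 and the SAP, and a tumor-specific definition is a legitimate choice. A reader might infer that other deaths have no status at all. The documents do not support that: the definition makes them non-events, and the open choice between censoring and competing risk is worth only 0.1-0.4 points under the 1-3% assumption. What stands is that the chosen event omits the deaths most relevant to the comparison, and that SAP 4.1 does not match it. The SAP 4.1 sentence may be shorthand for the DFS and OS models together, but it says neither.

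A reader might also infer that 3-year DFS will not be analysed. That goes too far. Protocol 12.3.2 plans to compare it by Kaplan-Meier curve and Cox model, and SAP 4.1 adds curves, a log-rank test and 95% CIs. What is missing is a written 3-year or 5-year estimate by arm, and a between-arm difference, with a CI.

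It can be said that every death is still captured by OS, and that deaths within 30 days are recorded as adverse events (protocol 9.1). This largely stands, but not without condition. Exit criterion 5 is worded broadly enough that an early death could be read as an exit, which would take the patient out of the mITT survival analyses. Nothing says that death is exempt.

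The OS time point in protocol 12.3.2 looks like a slip, since every other statement has 5 years.

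**Conclusion.** The point holds at moderate weight, for secondary endpoints only. DFS omits recurrence-free non-tumor deaths, SAP 4.1 describes the hazard ratio in terms that do not match, the named 3-year and 5-year results have no specified estimate, and protocol 12.3.2 has the wrong OS time point.

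The size rests on assumed rates: a gap of about 1-3 points in 3-year DFS if 1-3% die of other causes by 3 years, and more if that mortality is higher. The median thresholds depend only on the shape of the survival curve; that they will not be crossed is a judgement about this population. The documents do not support reading this as a threat to the SSI conclusion or the sample size, or as a DFS bias large enough to detect in 350 patients.

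**What to change.** - **SAP 4.1:** report Kaplan-Meier 3-year DFS and 5-year OS by arm, and the between-arm difference, each with a 95% CI, alongside the hazard ratio. The median can stay, shown as not reached where that applies.
- **Protocol 3.2.2(10), SAP 4.6 and SAP 4.1:** analyse DFS with death from any cause as an event, and name the event for each Cox model. Also report the prespecified tumor-death definition with non-tumor death as a competing event, and state how cause of death is determined.
- **Protocol 5.3 and SAP 4.2.1:** state that death is not an exit under criterion 5, so that these patients stay in the mITT survival analyses.
- **Protocol 12.3.2:** change the OS time point from 3 to 5 years.

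Timing matters. Protocol 6.2 allows unblinding once the main analysis is final, and that analysis follows the last patient's first month, years before the survival analysis. The change should be disclosed in any case. If it is made after unblinding, present both definitions side by side. Blinded classification of cause of death cannot be assured after that point.

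The cost is a short amendment. Deaths are already followed for OS, the existing definition already needs tumor deaths told apart from others, and the time-point estimates come from the same Kaplan-Meier fit. The downsides are a slightly lower reported DFS (about 1-3 points under the assumption above) and a definition in place since v1.0 that is changed or supplemented.

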4.7 Subgroup analysis

The subgroup analysis will be carried out only if the primary endpoint in the mITT population do not reach the non-inferiority margin. If the 95% CI of SSI is not within the non-inferiority margin, the primary endpoint will be summarized within the following subgroups.

- Sex (male, female);
- Age (≤ 65 years, > 65 years);
- Body Mass Index ($\leq 24 \text{ kg/m}^2$, $> 24 \text{ kg/m}^2$);
- Tumor site (distal transverse colon or splenic flexure of colon, descending colon,

proximal sigmoid colon);

- NRS2002 score (≤ 2 points, > 2 points);
- Mechanical bowel preparation (Yes, No);
- Oral antibiotic bowel preparation (Yes, No);
- Postoperative antibiotic use time(≥ 3 days, < 3 days);
- Operating time (≤ 180 mins, > 180 mins);

Subgroup analyses will be performed using mITT population. If intracorporeal anastomosis is proven to be noninferior to extracorporeal anastomosis regarding SSI, subgroup analysis will not be performed.

5 Missing data

Missing primary endpoint data will be treated as censored data and won't be imputed during analysis. Other missing data won't be imputed either. The missing data will be stated in the tables.

6 Interim analyses

No interim analyses are planned in this study.

7 Timing of analysis

We will conduct an analysis of the study's primary endpoint and publish the relevant findings after enrollment is completed and all patients have completed the first month of follow-up after surgery. When all patients complete 5 years of follow-up, the results involving survival data will be analyzed again, and the relevant research results will be published.

Reference

1. He L, Li M, Zhang J xin, Tong W hua, Chen Y, Wang Q. Surgical site infection after intracorporeal anastomosis for left-sided colon cancer: study protocol for a non-

inferiority multicenter randomized controlled trial (STARS). *Trials*. 2022 Nov 22;23(1):954.

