The STARS trial is a multicenter, randomized, single-blind, non-inferiority study designed to compare the incidence of surgical site infection (SSI) following intracorporeal anastomosis (IA) versus extracorporeal anastomosis (EA) in patients undergoing surgery for left colon cancer. The primary objective of this trial is to determine whether IA is non-inferior to EA in terms of SSI rates within 30 postoperative days. While the aims, hypotheses, and design of the STARS trial have been detailed elsewhere, this statistical analysis plan (SAP) will focus on the forthcoming analysis and presentation of the trial data. This SAP is conducted based on the study protocol version 2.1. The comprehensive study design, including the primary and secondary endpoints, along with the methods for determining sample size and the approach to data management, are integral to the SAP and are critical for understanding the trial's methodology and interpretation of results.

2 Study design and objectives

This is a prospective, multicenter, non-inferiority, two-arm, single-blind, randomized controlled study. The study aims to investigate the effects of intracorporeal anastomosis and extracorporeal anastomosis in laparoscopic-assisted radical left hemicolectomy on surgical site infection. It also examines the difference in postoperative recovery, safety, oncology outcomes and survival. The trial was prospectively registered in clinicaltrial.gov (NCT04201717) and the study protocol (version 1.0) has been previously published,(1) and minor revisions has been made in study protocol version 2.0 and version 2.1. Details of exclusion criteria and study treatments can be found in study protocol version 2.1.

3 Sample size

The sample size is determined based on the rate of SSI. Based on our multicenter retrospective data,(2) we estimated the incidence of overall SSI following EA in laparoscopic left hemicolectomy stands at 13.3%, while the incidence of SSI after IA is 8.0%. When there is an absolute risk difference in the SSI rate of more than 5%

within 30 days after surgery, IA is regarded as inferior to EA. Consequently, the sample size for this study is calculated based on non-inferiority, taking into account an absolute risk difference of 5%, a one-sided level of significance of 0.025, a ratio of 1:1, a power of 0.80, and a 20% drop-out rate. In total, 350 patients are required for this study, with 175 patients in the IA group and an equal number of 175 patients in the EA group.

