4.5 Primary endpoint

The primary endpoint in this trial is surgical site infection (SSI) within 30 postoperative days. Cases that fail to complete the 30-day follow-up are treated as missing data. The SSI will be compared between groups in the mITT population, PP population, and AT population.

- Overall SSI, Categorical variable. The absolute risk differences and the corresponding 95% CI between two groups will be calculated. The 95% CI will be compared with the non-inferiority margin (5%).

The subtypes of SSI (Superficial or deep incisional SSI, and Organ/space SSI) will also be compared between the two groups. However, their 95% confidence interval will not be compared with the non-inferiority margin.

The independent risk factors for overall surgical site infection (SSI) will be analyzed in the AT population. In univariable analysis, continuous variables will be converted to categorical variables. Chi-square tests or Fisher's exact tests will be employed. The key variables are as follows.

- Sex (male, female);
- Age (≤ 65 years, > 65 years);
- Body Mass Index ($\leq 24 \text{kg/m}^2$, $> 24 \text{kg/m}^2$);
- American Society of Anesthesiologists grading (I, II, III);
- Eastern Cooperative Oncology Group performance status score (0, 1, 2);
- Tumor site (distal transverse colon, splenic flexure of colon, descending colon, and proximal sigmoid colon);
- NRS2002 score (≤ 2 points, > 2 points);
- Parenteral prophylactic antibiotics (Yes, No);
- Mechanical bowel preparation (No, only enema, only oral laxative, enema plus oral laxative);
- Oral antibiotic bowel preparation (Yes, No);
- Postoperative antibiotic use time (≥ 3 days, < 3 days);

- Pathological TNM stage (0, I, II, III);
- Overflow of intestinal contents during anastomosis (Yes, No);
- Operating time (≤ 180 mins, > 180 mins);
- Blood loss during operation (≤ 100 ml, > 100 ml);
- Blood transfusion during operation (Yes, No);
- Prophylactic enterostomy (Yes, No);
- Anastomosis methods (Side-to-side anastomosis, End-to-side anastomosis, End-to-end anastomosis)
- Intervention (intracorporeal anastomosis, extracorporeal anastomosis)

Factors clinically relevant to SSI after univariable analysis will be included in multivariable analysis. Logistic regression will be used in multivariable analysis to identify independent risk factors for SSI. The effect size will be estimated using odds ratios (ORs) with 95% confidence intervals.

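### SAP 4.7 lets the primary result decide whether subgroups are reported: they are barred once non-inferiority is shown, and after a failure they are summarised without safeguards

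*Combined protocol and SAP*

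**What the plan says.** SAP 4.7 states the condition from both sides. Subgroups run after a failure: "The subgroup analysis will be carried out only if the primary endpoint in the mITT population do not reach the non-inferiority margin". They do not run after a success: "If intracorporeal anastomosis is proven to be noninferior to extracorporeal anastomosis regarding SSI, subgroup analysis will not be performed". When triggered, the work is described in one sentence: "If the 95% CI of SSI is not within the non-inferiority margin, the primary endpoint will be summarized within the following subgroups". The population is mITT.

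The list has nine factors: sex, age, BMI, tumour site (three levels), NRS2002 score, mechanical bowel preparation, oral antibiotic bowel preparation, postoperative antibiotic duration and operating time.

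Protocol 2.1, section 12, has no subgroup provision, so nothing there overrides the SAP. Neither document plans a treatment-by-factor interaction test. The nearest analysis is the risk-factor model of SAP 4.5: "Logistic regression will be used in multivariable analysis to identify independent risk factors for SSI". It uses the as-treated population and lists the intervention as one variable among 19.

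**The concern.** Whether a reader sees subgroup results should not depend on how the primary comparison turned out. The rule has a cost on each side.

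- **After a success**, intracorporeal anastomosis would be supported for every eligible patient, across four tumour sites and ages 18 to 80. The SAP then forbids any look at whether the effect is similar across them.
- **After a failure**, the endpoint is broken down over many small groups, and nothing says how those results may be used. SAP 4.5 does set a limit for the SSI subtypes: their intervals are not to be held against the margin. Section 4.7 has no such sentence for subgroups.

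At stake is how either outcome is interpreted, not the validity of the primary test.

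**Working it through.** **1. The plan's own sample size.** Inputs from SAP section 3: SSI 13.3% (EA) and 8.0% (IA), margin 5 points, one-sided 0.025, power 0.80, 20% drop-out. The distance to the margin is 0.05 + (0.133 − 0.080) = 0.103.

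n per arm = (0.133×0.867 + 0.080×0.920) × (1.960 + 0.842)² / 0.103² = 0.1889 × 7.849 / 0.01061 = 139.8, so 140.

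140 / 0.8 = 175 per arm, 350 in total. This matches the stated figure.

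**2. How often each branch occurs.** With 140 per arm the standard error is √(0.1889/140) = 0.0367. Power = Φ(0.103/0.0367 − 1.96) = Φ(0.84) = 0.80. At the planning rates subgroups are therefore barred about 80% of the time.

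**3. What the success branch can leave unseen (assumed heterogeneity).** Suppose IA has 18.3% SSI in a quarter of patients, against 13.3% with EA, and about 4.6% in the rest. The IA average is 0.25×18.3 + 0.75×4.57 = 8.0%, the planning rate. In 200,000 simulated trials non-inferiority was declared in about 82%. The SAP would not display the quarter that does worse.

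Reporting it would give a signal at best. With 35 per arm in that quarter, the half-width is 1.96 × √((0.183×0.817 + 0.133×0.867)/35) = 0.170, or 17 points.

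**4. Number of looks after a failure.** Eight factors with two levels and one with three give 8×2 + 3 = 19 levels. The seven factors fixed before surgery give 6×2 + 3 = 15.

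**5. What those looks show by chance.** The set-up is 140 per arm, the seven pre-surgery factors, no true heterogeneity, an overall Wald 95% interval and Newcombe intervals within levels. Subgroup sizes are assumed, because the documents give none; even and uneven splits were tried.

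| True SSI, EA v IA | Failed trials with ≥1 level whose upper limit is below 5 points | Failed trials with ≥1 level significantly harmful |
|---|---|---|
| 13.3% v 18.3% (IA at the margin) | about 16–18% | about 52–56% |
| 13.3% v 13.3% (equal) | about 42% | about 23% |

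Protocol 7.1 prescribes bowel preparation and oral antibiotics for all patients, so the No levels of those two factors may be nearly empty. With both at an assumed 97/3 split, the favourable-level figure in the first row is about 17%. With all nine factors, even splits and Wald intervals it is about 22%.

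**6. Precision.** At the planning rates the 95% half-width is 1.96 × 0.0367 = 7.2 points overall and 1.96 × √(0.1889/70) = 10.2 points at 70 per arm.

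**7. Whether the risk-factor model fills the gap.** It runs whatever the primary result and covers all nine subgroup factors. It groups patients by treatment received, and no interaction is stated. A main-effect odds ratio for the intervention cannot show whether its effect varies with tumour site, BMI or nutrition score.

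**The case against.** A reader might infer that the rule exists to rescue a failed trial, and that subgroups could never reveal harm. The documents do not support this. Section 4.7 says only that the endpoint is summarised; it plans no non-inferiority claim in any subgroup. Finding the source of a failure is an equally natural purpose. The table also points the other way: if IA is truly 5 points worse, a failed trial shows a significantly harmful level about three times as often as a favourable one.

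A reader might also take the 42% for equal arms as a false-claim rate. It is not. In that scenario IA is within 5 points in every level, so a level with an upper limit below 5 is correct and the overall failure is the error. The same holds at the planning rates, where the figure is about 66%. Only the scenario with IA at the margin measures a wrong message.

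It can fairly be said that the primary claim rests on the overall interval and does not need a subgroup check. Subgroups in a trial of this size are also weak evidence. At the planning rates with no heterogeneity, about 12% of successful trials would show some level, among all 19, with IA more than 5 points worse by chance. Both statements stand. They argue for an exploratory label and interaction tests. They do not argue for letting the result decide what is reported.

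**Conclusion.** The point holds as a reporting defect that should be corrected. The condition is explicit, is stated from both sides and is not overridden elsewhere. Once non-inferiority is declared (about 80% of trials at the planning rates), no check for a varying effect is allowed. After a failure, 19 levels are summarised without interaction tests, an exploratory label or a bar on using the margin. If IA is truly 5 points worse, roughly one failed trial in six would still show an apparently acceptable level, and about half would show a significantly harmful one.

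These frequencies rest on assumed subgroup sizes, independent factors and no true heterogeneity. The 82% illustration rests on an assumed pattern of effect. The defect itself depends on none of these. Sample size stays at 350, alpha at one-sided 0.025, and the decision rule is unchanged.

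**What to change.** Delete both conditional sentences in SAP 4.7 and state:

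> Subgroup analyses of the primary endpoint in mITT, for the listed factors fixed before surgery (sex, age, BMI, tumour site, NRS2002, mechanical bowel preparation, oral antibiotic bowel preparation), will be reported whatever the primary result, as risk difference with 95% CI and one treatment-by-factor interaction test per factor. They are exploratory, and no subgroup interval will be compared with the 5-point margin.

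Remove operating time and postoperative antibiotic duration from the list. Both arise after randomisation, and operating time is itself a secondary endpoint in SAP 4.6. The two bowel-preparation factors precede surgery but may follow randomisation, which protocol 7.4 places on the day before surgery; a footnote should say so.

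The cost is SAP wording and one forest plot, with no new data and no change to N or alpha. The downside is imprecise estimates and some chance findings, which the exploratory label and the interaction tests are there to contain.
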